7.0 STUDY DESIGN

This study is a prospective, single-center, randomized, double-blind, controlled trial in which 100 patients will be enrolled at the University of Wisconsin Hospitals and Clinics. The patients must satisfy the inclusion and exclusion criteria below. The patients will be randomized to receive bilateral PIFB with liposomal bupivacaine or bilateral PIFB with saline only. Recovery characteristics, including opioid consumption, pain scores, duration of mechanical ventilation, ICU length of stay, hospital length of stay, side effects, and chronic opioid use will be evaluated.

8.0 SUBJECT SELECTION

8.1 Inclusion Criteria

Each patient must meet all of the following inclusion criteria to be enrolled in the study.

1. The patient provides consent to participate in study.
2. The patient is 18-80 years old.
3. The patient's ideal body weight (IBW) is >50kg.
4. The patient is planned to undergo coronary artery bypass graft or single valve repair/replacement surgery via median sternotomy.
5. The patient is undergoing an elective procedure.

8.2 Exclusion Criteria

Patients meeting any of the following exclusion criteria are not to be enrolled in the study.

1. The patient is unable or unwilling to give consent.
2. The patient is non-English speaking.
3. The patient is known or believed to be pregnant or is currently breastfeeding.
4. The patient is a prisoner.
5. The patient is clinically unstable per discretion of the Investigator.
6. The patient requires urgent/emergent surgery.
7. The patient has a history of previous sternotomy.
8. Preoperative coagulopathy (INR >1.4, platelets <100,000) or ongoing anticoagulation or anti-platelet therapy (except aspirin 81mg).
9. The patient has an allergy or sensitivity to amide-type local anesthetics, dexmedetomidine or ketamine.
10. The patient has decompensated heart failure.
11. The patient has severe left ventricle dysfunction (defined quantitatively as an ejection fraction of less than or equal to 35%) or right ventricle dysfunction (defined qualitatively as "severe")
12. The patient has a diagnosis of cirrhosis or end-stage liver disease
13. The patient requires the use of mechanical circulatory support pre-operatively.
14. The patient uses chronic opioids (meaning at the time of the preoperative screening evaluation by the study team, the patient is prescribed and taking any opioid pain medication).

8.3 Vulnerable Populations

Prisoners

Due to the complexity of state and federal requirements governing the participation of prisoners in research, patients who are prisoners will not be considered for participation in this trial. In the unlikely event that a subject becomes a prisoner while participating in this trial, study procedures will stop and the subject will be returned to the clinical mode used prior to the intervention period or, if desired, an alternative mode requested by the clinical care team.

Pregnancy

Patients who are known to be pregnant will be excluded from participation.

8.4 Subject Identification

A member of the research team will review the surgery schedule at least one week in advance and identify patients who appear to be candidates for the study. The study team will work with the perioperative care team (including the assigned anesthesia staff and surgeon) to confirm eligibility criteria and potential participation. All protected health information used during the screening process of a potential subject will be the minimum necessary for the conduct of this study. Any protected health information recorded for

screening will be destroyed for ineligible patients once they are deemed ineligible by a study team member aside from the reason for exclusion. Any protected health information recorded for an eligible patient who declines study participation and is not enrolled in the study will immediately be destroyed.

8.5 Subject Recruitment and Informed Consent

When potential participants are identified and approved by the teams involved, a member of the study team will call the patient prior to the day of surgery and determine their interest in participating. On the day of surgery, potential participants will proceed through the usual preoperative process. A member of the study team will meet with the patients the morning of surgery. In order to ensure the candidate's privacy and confidentiality, the cubicle's curtain or room door will be closed. In a tone of voice insufficient for others to overhear the conversation and in the presence of only those immediately accompanying the patient and those who are directly involved with the patient's care, the candidate's eligibility, the study purpose, procedures, risks, benefits and alternatives will then be discussed. The written information about the study provided to the candidate at the time of their check-in will be reviewed and they will be instructed to take as much time as needed to consider their participation. Any questions that the candidate may have will be answered. Undue coercion will be prevented by stressing that the potential subject does not have to agree to participation and that the future care of the potential subject will not change regardless of the decision to participate. If the candidate has no further questions and would like to participate, they will be asked to sign the written informed consent document. The research subject will be given a copy of the signed and dated informed consent form. The original signed informed consent form is kept in a locked office in the Department of Anesthesiology.

8.6 Enrollment

A research subject will be defined as "enrolled" in the study when they meet the following criteria:

- The subject has been consented by study staff and has agreed to participate.
- The subject and study staff have completed all screening documentation.
- The PI has verified that the subject meets all of the inclusion criteria.
- The PI has verified that subject meets none of the exclusion criteria.
- The subject has been assigned to the protocol by study staff.
- The subject has been randomized.
- The subject has received the study intervention.

8.7 Early Termination and Withdrawal

At any point prior to or during the intervention period, the patient's clinical care team or a study physician may decide that the subject should be withdrawn from the study. In addition, at any point, a patient may elect to withdraw themselves from the study. If a patient is withdrawn from the study for any reason, the patient will then be followed according to standard of care follow-up. In the event that a subject is withdrawn from the study prematurely, the reason for withdrawal will be documented on a case report form.

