Statistical Methodology	
Data analysis will be performed on an intent-to-treat basis based upon assignment to a study arm. Continuous data will be compared using student T-test or Wilcoxon-rank sum testing as appropriate. Categorical data will be compared using Chi-square or Fisher exact testing as appropriate. The data will be presented graphically where possible using scatter plots, profile plots, or histograms. For all tests, statistical significance will be defined as a p-value less than 0.05.

Estimated Subject Duration	
The duration of the study for each subject is approximately 100 days.

Estimated Enrollment Period & Study Duration	
Study enrollment and follow-up will occur over 3 months with the total expected duration of the trial to be 24 months.

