9.2 Method for Assigning to Treatment Groups

After consent is obtained, participants will be randomized to an intervention group. Randomization will be accomplished using an online service (www.randomizer.org) and prefilling sealed envelopes determining each subject's intervention group. Randomization will occur immediately prior to the intervention. All subjects will receive the standard of anesthesia care appropriate for their surgery or procedure as determined by the primary anesthesia team caring for the subject, regardless of randomization group. Each study subject as well as the OR anesthesia team, cardiac surgery team, cardiothoracic ICU team, and nursing staff caring for the patient will be blinded to the study drug the patient received. However, the anesthesia provider performing the block (separate from the provider caring for the patient in the operating room) will not be blinded to the study drug injected and will have access to all monitors deemed appropriate by the primary team caring for the subject. In order to maintain blinding during the procedure, the medication syringe will be covered by a towel after being drawn up and during injection to prevent the intraoperative teams from visualizing the contents being injected. The ultrasound will also be turned such that only the anesthesiologist performing the procedure can see, as Exparel has a distinct sonographic appearance on injection. Specific individuals who were involved in the block placement will not perform any follow-up assessments or evaluations of the study patients for the remainder of the study.

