12.3 Subject Population(s) for Analysis

- Intention-to-Treat (ITT): all randomized subjects
- Safety Analysis Dataset: all randomized subjects who received the required study intervention.
- Protocol-compliant Population: all randomized subjects who received the required study intervention.

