12.5 Handling of Missing Data

Guidelines promulgated in the National Research Council report on handling of missing data will be followed^{28,29}.

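### Section 8.7 moves every withdrawn subject to standard-of-care follow-up without keeping study outcomes, although the analysis is ITT on all randomised subjects; the 90-day outcomes are most exposed

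*Combined protocol and SAP*

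**What the plan says.** **Withdrawal.** Section 8.7 provides that, before or during the intervention period, "the patient's clinical care team or a study physician may decide that the subject should be withdrawn from the study". The patient may also withdraw at any time. The consequence is the same in every case: "If a patient is withdrawn from the study for any reason, the patient will then be followed according to standard of care follow-up". The only item that 8.7 requires to be recorded is the reason: "the reason for withdrawal will be documented on a case report form".

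**Analysis set.** Section 12.3 defines "Intention-to-Treat (ITT): all randomized subjects", and the synopsis (3.1) agrees: "Data analysis will be performed on an intent-to-treat basis based upon assignment to a study arm". Section 12.3 also defines safety and protocol-compliant sets, both limited to randomised subjects who received the intervention.

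**Enrolment.** Section 8.6 lists the conditions for counting a subject as enrolled. The last is "The subject has received the study intervention".

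**Missing data.** Section 12.5 is one sentence: "Guidelines promulgated in the National Research Council report on handling of missing data will be followed".

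**Timing.** Section 9.2 states "Randomization will occur immediately prior to the intervention". The study activities listed after 10.2.7 place randomisation on the morning of surgery and the block after induction of anaesthesia.

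**The concern.** ITT needs two things: a set that contains everyone randomised, and outcome data for everyone in that set. The plan defines the set correctly. For withdrawn subjects it does not secure the data, because 8.7 hands them to routine care and asks only for the reason.

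The outcomes are not equally exposed. The 90-day call is made by the research team and is not part of routine care. Subjects moved to standard-of-care follow-up would therefore not be called, and 90-day pain and opioid use cannot be recovered later. In-hospital opioid use, pain scores and delirium assessments are in the chart whatever the subject's study status, but no rule says that they are still extracted after withdrawal.

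If these subjects drop out of the data, the result would be labelled ITT while omitting part of the randomised set. Losses that differ by arm and are related to outcome would then bias the comparison.

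**Working it through.** **1. Is there a retention rule elsewhere?**

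- 10.1 (footnote 1) and study activity 14: analgesic medication is recorded to 72 hours, with no condition that the block was given. Withdrawn subjects are not mentioned.
- 6.0: pain scores and CAM-ICU are standard-of-care assessments, so the data exist in the chart.
- Study activity 13: the 90-day call is a research-team procedure.
- 14.4: serious adverse events are recorded from consent through the 90-day call. This is a safety rule and does not cover efficacy outcomes.
- 12.5: cites external guidance and writes out no collection rule.

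None of these says that outcomes are still collected after withdrawal.

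**2. The plan's own figures (12.2, 12.4).** Mean 245 MME, SD 87, 25% reduction, two-sided alpha 0.05, power 90%, 1:1 allocation.

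- Target difference: 0.25 × 245 = 61.25 MME.
- n per group = 2 × (1.960 + 1.282)² × (87 / 61.25)² = 42.4, rounded up to 43. This reproduces the stated 43 per group (86 in total).
- The enrolment target of 100 leaves 14 subjects for dropout and incomplete data. No loss rate is given.

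**3. Illustrative bias in the primary endpoint, only if 8.7 is read as ending chart recording.** Assume that 50 treated subjects per arm are analysed, and that k further randomised subjects are lost from one arm, averaging s SD above the treated subjects in that arm.

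- Bias = s × 87 × k / (50 + k)
- SE = 87 × √(2/50) = 17.4
- Type I error = P(|Z + bias/SE| > 1.96), normal approximation

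| k (one arm) | s | Bias, MME | Share of 61.25 | Type I error |
|---|---|---|---|---|
| 1 | 1 | 87/51 = 1.7 | 2.8% | 5.1% |
| 2 | 1 | 174/52 = 3.3 | 5.5% | 5.4% |
| 3 | 1 | 261/53 = 4.9 | 8% | 5.9% |
| 5 | 1 | 435/55 = 7.9 | 13% | 7.4% |
| 7 | 1 | 609/57 = 10.7 | 17% | 9.4% |

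For k = 1 to 2 and s = 0.5 to 1.5, bias runs from 0.9 MME (0.5 × 87/51) to 5.0 MME (1.5 × 174/52), with type I error from 5.0% to 6.0%. Losses of 4 and 3 in the two arms with s = 1 give 87 × (4/54 − 3/53) = 1.5 MME and 5.1%. Equal losses with equal shifts give no bias. If the losses fall inside the 50 per arm instead, bias for k = 1 or 2 is 87 × k/50 = 1.7 or 3.5 MME, almost the same.

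**4. Price of keeping untreated subjects in ITT.** With 50 treated per arm plus u untreated active-arm subjects who get no block effect, the effect is 61.25 × 50/(50 + u). Power is from the two-sided t-test with 50 + u against 50 subjects.

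- u = 0: effect 61.25, power 93.6%
- u = 3: effect 57.8, power 91.6%
- u = 5: effect 55.7, power 90.1%

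The planned 90% is kept throughout this range.

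**5. 90-day outcomes.** The documents give no expected rates, variability or loss for these, so no bias figure can be derived.

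**The case against.** The case on the other side has real force, and most of it stands as a limit on the point.

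- **A missed block is not a withdrawal.** A reader might infer that 8.7 removes every subject whose block was not given. It does not say so. Section 12.3 keeps such subjects in ITT, and its separate protocol-compliant set has a purpose only if they stay there. The general recording rules and the 90-day call apply to an unblocked subject who has not been withdrawn.
- **Chart data survive.** A reader might infer that the primary endpoint is lost on withdrawal. Section 8.7 does not say that recording stops, and the 72-hour medication rule is unconditional. The loss needs the stricter reading.
- **Arm-related loss has few routes.** Section 9.2 blinds the patient, the operating-room and surgical teams and the ICU team, and randomisation comes just before the intervention. A withdrawal driven by the arm would mainly need the unblinded block provider or an acute reaction. Section 8.7 does not require the withdrawing study physician to be blinded, so the first route is narrow but open.
- **Part of the rule may be out of view.** The consent form is not in the text available for this review and may deal with data use after withdrawal. The guidance cited in 12.5 cannot be read here either. Neither puts a rule into 8.7, which is the section that staff would follow.
- **Contact must not be forced.** A patient who withdraws from the study may not wish to be telephoned. This stands, and the fix treats contact and data use separately.

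**Conclusion.** The point holds in a limited form and is minor. Section 8.7 is an operative instruction that conflicts with the data needs of an ITT analysis. Followed as written, it loses the 90-day call for withdrawn subjects, including those whom a clinician withdraws after randomisation and who have not themselves refused contact. These secondary outcomes are the main exposure, and its size cannot be computed from the documents.

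For the primary endpoint the expected bias is small. Given the short interval in 9.2, one or two losses is a reasonable assumption, and that gives 1.7 to 3.3 MME with type I error of 5.1% to 5.4%. This rests on three assumptions that the plan does not supply: 8.7 ends chart recording, all losses fall in one arm, and the lost subjects average 1 SD higher. Type I errors of 7% to 9% appear in the table, but they need five to seven losses all in one arm. Nothing in the documents supports that, and it should not be read as the likely size.

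Nor do the documents support the inference that 8.6 redefines the ITT set. Section 12.3 settles that set. Section 8.6 only adds ambiguity, because a randomised but untreated subject is in ITT without being counted as enrolled.

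**What to change.** Add to 8.7, in substance: for every randomised subject, including those withdrawn by a clinician and those whose block was not given or not completed, (a) opioid use from 0 to 72 hours and the other chart outcomes are collected unless the subject withdraws consent to data use; (b) the 90-day call is made unless the subject withdraws consent to contact; (c) all outcomes are analysed in the assigned arm. Record which of these consents, if any, was withdrawn, and report withdrawals by arm and reason.

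Optionally, note in 8.6 that enrolled is an accrual count and does not define the ITT set. The count need not move to randomisation. With a fixed 50 randomised per arm, the effect would be 61.25 × (50 − u)/50, and power would fall to 90.6% for u = 3 and 88.0% for u = 5.

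The cost is a short addition to 8.7, some chart abstraction, a few telephone calls and the slight dilution of the ITT effect shown in the working. The sample size does not change. The addition has to be made prospectively, because missed 90-day calls cannot be made up later.

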9.0 PROCEDURAL INTERVENTION

9.1 Study Procedural Intervention(s) Description

The intervention portion of this study is the randomized assignment (1:1) to receive 25mL of saline or 15mL of 0.25% bupivacaine mixed with 10mL of liposomal bupivacaine (133mg) as a single-shot injection into the pecto-intercostal fascial plane bilaterally. All studied volumes are well within the acceptable range for pecto-intercostal nerve blocks described previously. All patients will be treated intraoperatively according to our institutional enhanced recovery after surgery for cardiac patients, including the use of dexmedetomidine and ketamine infusions with as-needed fentanyl intravenous dosing.

9.2 Method for Assigning to Treatment Groups

After consent is obtained, participants will be randomized to an intervention group. Randomization will be accomplished using an online service (www.randomizer.org) and prefilling sealed envelopes determining each subject's intervention group. Randomization will occur immediately prior to the intervention. All subjects will receive the standard of anesthesia care appropriate for their surgery or procedure as determined by the primary anesthesia team caring for the subject, regardless of randomization group. Each study subject as well as the OR anesthesia team, cardiac surgery team, cardiothoracic ICU team, and nursing staff caring for the patient will be blinded to the study drug the patient received. However, the anesthesia provider performing the block (separate from the provider caring for the patient in the operating room) will not be blinded to the study drug injected and will have access to all monitors deemed appropriate by the primary team caring for the subject. In order to maintain blinding during the procedure, the medication syringe will be covered by a towel after being drawn up and during injection to prevent the intraoperative teams from visualizing the contents being injected. The ultrasound will also be turned such that only the anesthesiologist performing the procedure can see, as Exparel has a distinct sonographic appearance on injection. Specific individuals who were involved in the block placement will not perform any follow-up assessments or evaluations of the study patients for the remainder of the study.

9.3 Unblinding Procedures

To minimize the safety risk associated with blinding, the anesthesiologist performing the block will be available to be contacted by other caregivers for unblinding in the situation where that becomes necessary for patient safety. The anesthesiologists, surgeons, intensivists and nursing staff will be aware that the patient is enrolled in a study and may have received bupivacaine with liposomal bupivacaine injections.

10.0 STUDY CALENDAR, MEASUREMENTS, AND ACTIVITIES

10.1 Study Calendar

	Screening Visit 1 Phone/ inperson visit	Procedure Visit 2	ICU Visit 3	24- hours Post-op Visit 4	48-hours Post-Op Visit 5	72-hours Post-op Visit 6	3 Months or 90 days after DOS (Phone)
Window	Up to 60 days before surgery	Morning of Surgery	Followi ng surgical proced ure	24 hours post-op +/- 6 hours	48 hours post-op +/- 6 hours	72 hours post-op +/- 6 hours	
Screening	X						
Eligibility	X	X					

Informed Consent	X	X					
Demographics	X						
Medical History	SOC						
Randomization and Intervention: Pecto- Intercostal Fascial Plane Blocks vs Sham (control)		X					
Electronic Data Collection (EDC)		X	X	X	X	X	
Brief Pain Inventory Form							X
Concomitant Medications ¹		SOC	X	X	X	X	X
Adverse Events		SOC		SOC			

¹ All medications taken for analgesia at home regularly, prior to arrival on the day of surgery, and perioperatively (until 72 hours postoperatively) will be recorded.

². EDC will all capture the opioid intake, pain measurement and all other relevant study information that is not capture during the study procedures.

10.2 Study Measurements

10.2.1 Preoperative Period - Screening (Visit 1)

- Age
- Sex
- Height
- Weight
- Body mass index
- Date of surgery
- Procedure
- Indication for procedure
- Baseline creatinine

- Baseline INR
- Baseline platelet count
- Preoperative anticoagulation
- Baseline left ventricle ejection fraction
- Baseline qualitative right ventricular function
- Presence of cirrhosis or end-stage liver disease diagnosis
- Presence of preoperative opioid use
- Baseline pain score (Numeric rating scale [NRS])

10.2.2 Intra-operative Period (Visit 2)

- Surgery length
- Intraoperative opioid consumption
- ASA Status

10.2.3 Postoperative Period – ICU (Visit 3)

- Opioid consumption
- Pain scores (Critical Care Pain Observation Tool [CPOT], numeric rating scale [NRS]) q 4 hours
- Time until first rescue opioid analgesia
- Time until extubation
- Time until return of bowel function
- CAM-ICU q 8-12 hours
- ICU length of stay

10.2.4 Postoperative Period - 24 hours (Visit 4)

- Opioid consumption
- Pain scores (CPOT, NRS) q 4 hours
- Time until first rescue opioid analgesia
- Time until return of bowel function, recorded as time to first documented bowel movement
- CAM-ICU q 8-12 hours

